#### 9.5.4 Locator Form

This includes self-reported contact information for participants and information necessary for registration in OnCore, including full name, address, phone number(s), email address, and date of birth. It also asks participants their preferred mode of communication with the study team (phone, text, or email). It is estimated that these questions ([Appendix 31.04](#)) will take approximately 1-3 minutes to complete.

#### 9.5.5 Caregiver Quality of Life (QoL)

We will use the CareGiver Oncology QoL questionnaire (CarGOQoL), a 29-item, well-validated instrument specific to caregivers for patients with cancer, to measure family caregiver QoL in multiple domains. It is estimated that the CarGOQoL ([Appendix 31.05](#)) will take approximately 2-4 minutes to complete.

#### 9.5.6 Caregiving Burden

Caregiving burden will be measured using the Caregiver Reaction Assessment (CRA). It is estimated that this tool ([Appendix 31.06](#)) will take approximately 3-5 minutes to complete

#### 9.5.7 Self-Efficacy

We will use the Lewis Cancer Self-Efficacy Scale (CASE) to measure caregivers' confidence in managing the impact of their loved one's illness. The CASE questionnaire is included as [Appendix 31.07](#) and will take approximately 2-4 minutes to complete.

#### 9.5.8 Perceived Coping Skills

We will use the Measure of Current Status (MOCS) to assess caregivers' self-perceived status on skills targeted by the intervention including ability to relax, recognizing stress-inducing situations, restructuring maladaptive thoughts, and coping. The MOCS is included as [Appendix 31.08](#). It is estimated that the MOCS will take approximately 2-4 minutes to complete.

#### 9.5.9 Qualitative Exit Interview

We will use a semi-structured interview guide that will explore 1) caregiver perception of the acceptability and content of the intervention; and 2) caregiver perceptions of the benefits of receiving the intervention. Facilitators will use probes to obtain comprehensive understanding of the caregivers' perspectives. The semi-structured interview guide is detailed in [Appendix 31.09](#). The interview will last approximately 30 minutes.

### *9.6 Description of Intervention*

We utilized the findings from our longitudinal and qualitative studies and a thorough review of the literature to identify the necessary components of our planned caregiver intervention. The preliminary content includes three essential components: 1) a psychoeducational component to address preparedness, manage expectations, and develop caregiving skills; 2) a psychosocial component focusing on coping strategies, mindfulness, and facilitating acceptance while living with uncertainty; and 3) a self-care

component to promote caregiver health and well-being. We anticipate that the psychological intervention will consist of six individual sessions (45 minutes each), which will provide sufficient dose to promote effective coping and reduce caregiving burden. Whenever possible, we will coordinate sessions with hospital and clinic visits or conduct them via phone or video conference (using a HIPAA-compliant video platform provided by MGH TeleHealth) to minimize participant burden and facilitate adherence. The intervention will be delivered by a social worker or psychologist in the MGH Cancer Center, specifically trained on the intervention content and delivery. Interventionists may contact caregivers directly via text message, phone call, or email to coordinate session scheduling only. No identifying information will be shared via text or email; these will be used solely for scheduling purposes. In the Locator Form ([Appendix 31.04](#)), participants will be asked to indicate their preferred method of communication (phone call, text, or email), and the study team will use this response to determine how to contact participants. In this pilot study, we will enroll 25 caregivers of patients with malignant gliomas to assess fidelity and acceptability of the intervention. Attached as [Appendix 31.15](#) is the Intervention Manual for our Psychological Intervention for Caregivers of Patients with Malignant Gliomas, which will be used as the basis for the intervention. We have refined the intervention to tailor it to the needs specific to this population of caregivers, based on our qualitative interview data.

### *9.7 Instrument Administration*

A member of study staff trained in qualitative interviewing will facilitate the interviews over the phone or in person using a semi-structured interview guide with open-ended questions and response probes ([Appendix 31.09](#)), and the interview will last approximately 30 minutes. All interviews will be audio-recorded; study staff will ask for permission to turn on the audio-recorder prior to beginning each interview. A script for administration of the qualitative interview over the phone is included as [Appendix 31.14](#).

The brief enrollment survey (Appendices [31.03](#), [31.04](#)) and the 7-item Generalized Anxiety Disorder measure ([Appendix 31.01](#)) may be completed by participants via mail correspondence, online using a secure website (REDCap), over the phone, or in clinic at MGH, in accordance with participant preferences and availability. The message templates for administration of the GAD-7 and enrollment survey by mail and REDCap are included as Appendices [31.11](#) and [31.12](#), respectively. A script for survey administration over the phone is included as [Appendix 31.13](#). Only participants who have a GAD-7 score  $\geq 5$  will be registered in OnCore and complete the qualitative interview. Caregivers with GAD-7 scores  $< 5$  will be considered ineligible for the study. If a caregiver is ineligible based on his or her GAD-7 score but is still interested in the study, we will re-approach in 3 months and re-administer the GAD-7.

## **10.0 Data and Specimen Banking**

N/A

## **11.0 Data Management and Confidentiality**

### *11.1 Sample size and power calculations*

We will recruit and consent 25 caregivers for the open pilot. We chose the sample size of 25 caregivers based on the feasibility of completing the project in a timely fashion, given the rarity of this disease. It is

expected that it will take approximately twelve to eighteen months to complete accrual for the study. The proposed sample size is also sufficient to provide us with preliminary data that can be utilized to determine the effect size and adequately power a multi-center randomized controlled trial in the future.

## 11.2 Analysis Plan

Feasibility will be defined by rates of enrollment and participation. We will report the proportion of eligible caregivers who agree to participate in the intervention and the proportion of intervention visits completed by each participant. Additionally, we will examine reasons for declining participation, incomplete session attendance, and early withdrawal from the study. The intervention will be deemed feasible if at least 70% (+/- 18%) of eligible caregivers are enrolled in the study and if at least 70% of enrolled participants complete  $\geq 50\%$  of the sessions. We will use descriptive statistics to summarize the demographic and clinical characteristics of caregivers enrolled in the study. We will audio-record and transcribe the individual semi-structured exit interviews and analyze qualitative data according to NIH Best Practices for Mixed Methods Research in the Health Sciences. Study staff will independently review the transcripts to create a thematic framework for interpretation. Two individuals, including the Principal Investigator, will independently code the data to enhance validity and credibility, until high reliability is achieved (Kappa>0.80). The planned sample size will allow us to collect comprehensive feedback and ensures sufficient number of participants to achieve thematic saturation. In an exploratory analysis, we will also examine changes in caregiver-reported outcomes from baseline to post-intervention using paired t-tests.

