##### *9.2 Enrollment*

A member of study staff (e.g. PI, Research Assistants) will obtain informed consent in person prior to initiating any study measures. Participants will be consented next time they are in clinic. Research

assistants, all of whom previously have received CITI and consent training, will be provided study-specific recruitment training. Caregivers who would like more time to consider participation at in-clinic approach are able to take the consent forms home with them to review. Caregivers will be provided with study staff contact information if any questions or concerns regarding the research arise.

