### *9.3 Registration*

Study staff will register eligible participants in the Clinical Trials Management System (CTMS) OnCore as required by DF/HCC SOP REGIST-101 after the participant completes the brief enrollment survey. Caregivers who report GAD-7 scores  $<5$  will be considered ineligible for the study and will not be registered in OnCore. If a caregiver's GAD-7 score renders them ineligible but they are still interested in the study, we will re-approach them in 3 months to re-administer the GAD-7. Caregivers who do not complete the brief enrollment survey will not be registered in OnCore.

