## **23.0 Local Number of Subjects**

A total of 25 subjects (excluding screen failures) will be accrued locally. We expect more than 50% to demonstrate at least mild anxiety (GAD-7 score of 5 or greater) so total accrual of no more than 50 caregivers including screen failures should be necessary.

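### The enrollment criterion carries an unexplained ±18% that fits a denominator of 25, not the number of eligible caregivers, and it leaves the 70% floor open to two readings

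*Combined protocol and SAP*

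**What the plan says.** Section 8.0 makes feasibility the primary endpoint, and Section 11.2 holds its only decision rule. The rule has two parts:

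- Enrollment: "The intervention will be deemed feasible if at least 70% (+/- 18%) of eligible caregivers are enrolled in the study".
- Session completion: "if at least 70% of enrolled participants complete" at least half of the sessions.

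The ±18% appears once, on the first part only. The text gives no confidence level, method, denominator or role in the decision. References 31-34 are attached to the sentence, but nothing in the plan says that the figure comes from them.

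The same section describes the enrollment rate: "We will report the proportion of eligible caregivers who agree to participate in the intervention". Its denominator is therefore the eligible caregivers.

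On sample size, Section 11.1 says "We will recruit and consent 25 caregivers for the open pilot", and Section 23.0 says "A total of 25 subjects (excluding screen failures) will be accrued locally". Section 11.1 justifies 25 by practicality and by its use for planning a later trial. It contains no precision calculation. The expected number of eligible caregivers is not stated.

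**The concern.** There are two problems with the margin.

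First, it appears to have been computed with the wrong denominator for the proportion it is attached to. Twenty-five caregivers are to be enrolled, so 25 is the base for session completion. The enrollment rate has a larger base whenever an eligible caregiver declines.

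Second, a symmetric margin has no clear meaning inside an at-least rule. As a precision statement it is harmless to the decision. As a tolerance it lowers the floor to 70 − 18 = 52%. Because this sentence alone decides whether the pilot is called feasible, the rule should not have to be interpreted once the data are known.

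**Working it through.** **Inputs.** Threshold 70% and margin ±18% (Section 11.2); 25 enrolled, excluding screen failures (Section 23.0). The 95% level and the normal approximation are assumptions, because the plan gives neither.

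**Step 1: reproduce the plan's figure.** Half-width = 1.96 × √(p(1 − p)/n). With p = 0.70 and n = 25:

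1.96 × √(0.21/25) = 0.1796, or 18 points.

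Solving for the n that gives exactly 0.18: n = 1.96² × 0.21/0.18² = 24.9. Half-widths that round to 18 correspond to n from 23.6 to 26.3. Other choices at n = 25 do not round to 18:

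| Choice at n = 25 | Half-width (points) |
|---|---|
| 95% normal approximation, p = 0.70 | 18.0 |
| 90% normal approximation, p = 0.70 | 15.1 |
| 99% normal approximation, p = 0.70 | 23.6 |
| 95% with continuity correction, p = 0.70 | 20.0 |
| 95% normal approximation, p = 0.50 | 19.6 |
| 95% Wilson, 18/25 | 16.7 |
| 95% Clopper-Pearson, 18/25 (average of the two sides) | 18.7 |

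At other levels, ±18% would need n = 17.5 (90%) or n = 43.0 (99%). Neither matches a count in the plan.

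**Step 2: which proportion has denominator 25?** Session completion does. For the enrollment rate, a denominator of 25 with 25 enrolled means that no eligible caregiver declined, which is a rate of 100% and not 70%.

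**Step 3: half-width for the enrollment rate.** With 25 enrolled at 70%, the eligible number 25/0.70 = 35.7, about 36.

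1.96 × √(0.21/36) = 0.1497, or 15 points.

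If the 25 enrolled are taken as fixed and the number eligible as random, the inverse-binomial form gives 1.96 × 0.70 × √(0.30/25) = 0.150, the same answer. The stated margin is thus about 18 − 15 = 3 points too wide for this proportion.

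**Step 4: what the two readings of the floor would do with 25 enrolled.**

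| Eligible | Enrollment rate | 70% floor | 52% floor |
|---|---|---|---|
| 35 | 25/35 = 71.4% | met | met |
| 36 | 25/36 = 69.4% | not met | met |
| 48 | 25/48 = 52.1% | not met | met |
| 49 | 25/49 = 51.0% | not met | not met |

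The readings disagree for 36 to 48 eligible caregivers.

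**Step 5: illustration at one assumed true enrollment rate, 60%** (the plan gives none).

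- Recruiting until 25 enroll: the 70% floor is met if 25 enroll among the first 35 eligible, P(Bin(35, 0.60) ≥ 25) = 0.112. The 52% floor is met if 25 enroll among the first 48, P(Bin(48, 0.60) ≥ 25) = 0.897.
- Fixing 36 eligible instead: P(Bin(36, 0.60) ≥ 26) = 0.090 for the 70% floor and P(Bin(36, 0.60) ≥ 19) = 0.854 for the 52% floor.

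**The case against.** The best defense is that the rule says at least 70%, so 70% is the floor and the ±18% only states precision. On that reading no feasibility verdict changes. What remains is a margin about 3 points too wide, which errs on the cautious side. It is also possible that the margin was meant for both criteria and written once, beside the first 70%. The level and method behind it are inferred, and the cited references are not available to settle intent. Section 11.2 commits to reporting the enrollment proportion and the reasons for declining, so readers of the results can judge the rate for themselves. This is a single-arm pilot of 25.

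Most of this stands. It limits the consequence but does not remove the defect: the margin is unlabeled, does not fit the proportion it is attached to, and sits inside the decision threshold.

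A reader might go further and infer that the sponsor intends to accept enrollment as low as 52%. The documents do not support that. Nothing calls the margin a tolerance, and its match to a confidence half-width points the other way. Nor do the probabilities in Step 5 forecast this trial: they rest on an assumed rate, vary with the stopping method, and concern one of two criteria that must both be met.

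Who belongs in the eligible denominator is a separate question. Study staff "will obtain informed consent in person prior to initiating any study measures", so a caregiver who declines has no GAD-7 score. That would need an answer even without the ±18%, and the present point does not depend on it.

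**Conclusion.** The point holds as a misfitting and unlabeled margin inside the primary endpoint's decision rule. Assuming a 95% normal-approximation interval and 25 enrolled, ±18 points describes session completion. The enrollment rate at 70% would have a half-width of about 15 points on about 36 eligible caregivers, a number derived here and not stated in the plan.

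If 70% is the floor, which is the more likely intent, the effect is confined to that modest overstatement of uncertainty. The ambiguity matters only if the margin is applied as a tolerance. In that case, 25 enrolled from 36 to 48 eligible would reverse the verdict on this criterion, and at an assumed 60% true rate the chance of meeting it would be about 90% instead of 11% (85% instead of 9% with 36 eligible fixed). The harm is limited to the feasibility label and the stated precision, but the rule should be corrected because it is the only one for the primary endpoint.

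**What to change.** In Section 11.2, delete the ±18% from the decision rule and state the rule on observed proportions, for example: *The intervention will be deemed feasible if the observed proportion of eligible caregivers who enroll is at least 70% and the observed proportion of enrolled participants who complete at least 50% of sessions is at least 70%. 95% confidence intervals will be reported for both proportions, using their actual denominators.* Name the interval method.

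If an expected precision is kept, put it in a separate sentence that is not part of the rule: about 18 points for session completion (n = 25) and about 15 points for enrollment (about 36 eligible), each at 70% with a 95% normal-approximation interval.

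The cost is a short wording edit and one added interval per proportion in the report. The sponsor's 70% thresholds, the sample size, the conduct of the study and the data collection are unchanged.

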## 11.3 Data Collection

Data will be collected primarily in the form of caregiver interviews. Interviews will be audio recorded on a digital recorder, and the audio files will be stored in an encrypted computer drive on the secure Partners network. Caregivers will complete the 7-Item Generalized Anxiety Disorder scale (GAD-7) to determine whether they are eligible to participate in an interview. We will also gather demographic and contact information about our sample via a brief enrollment survey. Specifically, we will collect data on:

Data	At screening	Pre-Intervention	Post-Intervention
7-Item Generalized Anxiety Disorder (GAD-7)	X		
Demographics	X		
Locator Form (Contact Information)	X		
Hospital Anxiety and Depression Scale (HADS)		X	X
CareGiver Oncology QoL questionnaire (CarGOQoL)		X	X

Caregiver Reaction Assessment (CRA)		X	X
Lewis Cancer Self-Efficacy Scale (CASE)		X	X
Measure of Current Status (MOCS)		X	X
Qualitative Exit Interview			X

To safeguard participant information and confidentiality, all data will be stored in locked cabinets in study staff's offices, in password-protected computer files, and in REDCap databases, all of which are accessible only to trained and IRB-approved study staff. Participants' data will be identified by an ID number only, and a link between names and ID numbers will be kept separately under lock and key or in a separate password protected document accessible only by study staff.

As part of the NIH data sharing directive, deidentified data from this study will be transferred to the PCRC De-identified Data Repository located at the University of Colorado. Any deidentified data that are collected and entered will remain in the PCRC Data Repository indefinitely. All future data analysis will be performed on de-identified data in the PCRC Data Repository. While the information and data resulting from this study may be presented at scientific meetings or published in a scientific journal, participant identities will not be revealed. Data will be presented in aggregate reports without patient-level identifiers.

Consistent with the PCRC Data Sharing Policy, the data from this study will be deidentified and will be transferred and stored on a server maintained by the PCRC at the University of Colorado (U of CO). U of CO's Office of Information Technology (OIT) Department provides University employees with centralized file sharing services. Centralized file servers are Windows-based virtual systems hosted in OIT's vmware server environment. These servers are proactively monitored by the automated monitoring system, patched on a monthly basis with latest security patches and updates, and backed up nightly by OIT's Enterprise backup solution, consistent with good data storage practices.

## **12.0 Provisions to Monitor the Data to Ensure the Safety of Subjects**

N/A. This study does not involve more than Minimal Risk to subjects.

## **13.0 Withdrawal of Subjects**

We do not anticipate that any research participants will be withdrawn from the study without their consent. If a participant requests withdrawal from the study, we will ask them if they are comfortable sharing the reason for withdrawal to ensure that there are no adverse events to report to the IRB. We will ask the study participant if they are still willing to permit the study team to continue to monitor their health record, but withdraw from all other study procedures.

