#### **9.5.2 Hospital Anxiety and Depression Scale (HADS)**

We will use the Hospital Anxiety and Depression Scale (HADS) to assess symptoms of depression and anxiety in all study participants. The HADS is a 14-item questionnaire that contains two 7-item subscales assessing depression and anxiety symptoms during the past week ([Appendix 31.02](#)). Used extensively in samples of patients with cancer and their caregivers, the questionnaire consists of a four-point item response format that quantifies the degree to which participants experience mood symptoms. Scores on each subscale range from 0 to 21, with a cutoff of 8 or greater denoting clinically significant anxiety or depression. The estimated time for completing this scale is 2-5 minutes.

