## **14.0 Risks to Subjects**

We do not anticipate that participants in the psychological intervention or qualitative interviews will experience any serious adverse reactions. If a participant expresses distress during the psychological intervention visits or exit interviews, they will be reassured by the psychologist and the research staff that

they can stop the intervention and they need not answer any of the interview questions which they find upsetting. They will also be reminded that study participation is voluntary. If participants remain distressed, both the Principal Investigator and the oncologist will be notified. Additionally, we will offer participants who remain distressed an opportunity to meet with either the principal investigator ([name]) or a clinical psychologist ([name], a co-investigator) to help address their distress. Should participants require further support, we will offer them an opportunity to meet with the MGH Neuro Oncology Clinic social worker for additional follow-up.

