### 31.09 Qualitative Exit Interview

#### INTRODUCTION

You recently took part in a study that was designed to help caregivers of with brain tumors cope most effectively with their loved ones' illness. We are now interested to know about your satisfaction with different aspects of this research study so that we continue to shape how to provide it to patients. There is no right or wrong answer. Your answers will be kept confidential and will not affect your participation in future research studies or your access to medical care.

First, I am going to ask you some questions about the timing of the sessions you had and how they were delivered.

1. This study was scheduled to start within 6 months after your loved one's diagnosis. How do you feel about the timing of the program?

- A. Right time
- B. Too early in treatment
- C. Too late in treatment

Additional Comments:

2. This study was scheduled to continue for 6 weeks. How do you feel about the length of the program?

- A. Right time
- B. Too short
- C. Too long

Additional Comments:

3. What prevented you from attending the intervention sessions? What would help you attend more of these sessions?

4. The research study was designed so that sessions can be scheduled over the phone or through telemedicine (videoconference) when in-person visits were not possible. How do you feel about the phone or video sessions?

- A. Great
- B. In-person was better
- C. Not sure

Additional Comments:

Additional Probe: Would you have preferred all sessions to be delivered over the telephone or telemedicine for convenience?

5. How do you feel about the total number of visits included in this research study (six visits total)?

- A. Right amount

Additional Comments:

B. Too few	
C. Too many	

6. How do you feel about the amount of time each session lasted?

A. Right amount	Additional Comments:
B. Too short	
C. Too long	

Now I am going to ask you some questions about the material covered in your visits.

7. During these sessions, you may have learned about strategies to help you cope most effectively with your loved ones' illness. How helpful did you find these strategies?

A. Helpful	Additional Comments:
B. Not helpful	
C. Not sure	

Additional Probe: The interviewer can remind the caregiver about specific strategies such as acceptance, mindfulness, problem-solving, self-care, communication techniques, etc. Also ask which of these strategies was the most helpful

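### The protocol actively asks about adverse events only when a caregiver requests withdrawal; one question at the exit interview would cover those who stay in

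*Combined protocol and SAP*

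**What the plan says.** - **Section 12.0** (safety monitoring) is marked not applicable because the study is minimal risk.
- **Section 13.0**: a caregiver who requests withdrawal is asked whether they are comfortable "sharing the reason for withdrawal to ensure that there are no adverse events to report to the IRB". No other section links an enquiry to adverse events.
- **Section 14.0** sets out a stepped response that starts on the condition "If a participant expresses distress during the psychological intervention visits or exit interviews". It runs from reassurance, through notifying the principal investigator and oncologist, to an offered meeting with the investigator or a psychologist, and then social work. It schedules no enquiry and describes no log or tally.
- **Appendix 31.09** (exit interview) tells the caregiver: "We are now interested to know about your satisfaction with different aspects of this research study". Item 3 asks "What prevented you from attending the intervention sessions". Item 16 asks about anything else that did not help, and item 21 is open. Section 9.5.9 adds: "Facilitators will use probes to obtain comprehensive understanding of the caregivers' perspectives".
- **Section 11.2**: "we will examine reasons for declining participation, incomplete session attendance, and early withdrawal from the study". As an exploratory analysis, "we will also examine changes in caregiver-reported outcomes from baseline to post-intervention using paired t-tests". Section 11.3 shows the HADS among the measures taken before and after the intervention.

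**The concern.** Everyone enrolled has a GAD-7 score of at least 5, and the protocol itself foresees both distress in sessions and adverse events that may need reporting. Yet the active question goes only to people who are leaving. If no event is recorded among those who complete, the report cannot separate none having occurred from none having been asked about.

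The single aim in 1.2 is to refine the intervention and protocol from exit feedback, and section 2.1 says the findings may inform a randomized trial. Whether some caregivers felt worse is part of that feedback. It is easy to obtain at exit and hard to recover later.

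**Working it through.** **1. Routes by which an event could become known**

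| Route | Who it reaches | Asks about harm? |
|---|---|---|
| 13.0 reason for withdrawal | Those who request withdrawal and agree to answer | Yes, by stated purpose |
| 14.0 distress pathway | Those who express distress in a session or exit interview | No; reactive |
| 9.6 individual sessions (six of 45 minutes) | Attenders | Not in the protocol text; manual not seen |
| 20.1 weekly meetings of investigator and staff | Passes on what staff have noticed | No |
| 9.2 staff contact details | Caregivers who make contact | No; volunteered |
| 31.09 items 3, 16 and 21, with probes | Interviewees | No; barriers, unhelpful content, open comment |
| 11.2 review of reasons | Decliners, partial attenders, leavers | No; feasibility |

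Only the first row is an active enquiry about adverse events, and it excludes those who stay.

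**2. What a tally could show**

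The plan gives no figure on harm to reproduce. Its one precision figure, ±18% in 11.2, is 1.96 × √(0.7 × 0.3 / 25) = 0.180. It is correct and not at issue here.

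Input: 25 caregivers (11.1). The 20 used below is an assumed number answering.

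- Zero events, exact two-sided 95% upper limit = 1 − 0.025^(1/n). For n = 25 this is 13.7%; for n = 20 it is 16.8%.
- 5 of 25 = 20%, exact (Clopper-Pearson) 95% CI 6.8% to 40.7%.
- Chance of at least one case at an assumed true rate of 10%, if every case is reported: 1 − 0.9^25 = 93%.

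The tally is imprecise but likely to show a problem that is not rare.

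**3. Do the paired t-tests already cover this?**

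They test a mean. In an assumed example, 20 caregivers improve by 3 points and 5 worsen by 4:

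- mean = (20 × (−3) + 5 × 4) / 25 = −1.6
- SD = 2.858; t = −1.6 / (2.858 / √25) = −2.80 on 24 df; p = 0.010, with 20% worse.

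This is a property of any comparison of means. It shows that the t-tests do not replace the question, not that they are wrong.

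**4. Would a count from the HADS serve instead?**

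Section 9.5.2 describes each subscale "with a cutoff of 8 or greater denoting clinically significant anxiety or depression", so counting moves from below 8 to 8 or more is tempting. The documents give no baseline distribution. I assumed baseline mean 8 to 11 on HADS-A and 5 to 7 on HADS-D, baseline SD 3.5, SD of change 3 to 4, correlation of changes 0 or 0.7, zero true mean change, and rounded scores.

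- Share already at 8 or more on HADS-A = Φ((mean − 7.5) / 3.5). Mean 8 gives Φ(0.143) = 56%; mean 11 gives Φ(1) = 84%. These caregivers cannot cross on the anxiety subscale.
- Simulated share crossing on at least one subscale by chance alone: about 15% to 26%. That is 0.15 × 25 ≈ 4 to 0.26 × 25 ≈ 7 caregivers.

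Counting any rise is worse. With zero mean change and the same SDs, and correlation from 0 to 0.7, 56% to 70% rise by at least 1 point on at least one subscale. Neither count is a usable harm measure here.

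**The case against.** The case for leaving the plan alone is fair. This is a talking intervention judged minimal risk. A trained clinician sees each caregiver individually, staff meet the investigator weekly, every caregiver has contact details, and 14.0 gives a clear stepped response. Interviewers probe, and item 16 invites negative comment. The manual, the consent form and the institutional procedures were not available, and any of them could hold a systematic check. No stated aim or endpoint depends on a harm count. All of this stands, and it keeps the point small. It does not change the fact that, in the protocol text, no route asks those who stay whether they were harmed or felt worse.

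A reader might infer three stronger conclusions, which the documents do not support:

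- **That harm would go undetected.** The indirect routes are real, and the manual is unseen.
- **That 11.2 is faulty for naming only paired t-tests and no count of worsened caregivers.** The analysis is labelled exploratory, and the paired scores are collected, so individual change can still be derived. The missing count is a detail, not an error.
- **That a HADS cutoff count should be prespecified as a harm measure.** Under the assumptions in step 4 it would mostly reflect chance, and it would miss many of the most anxious caregivers.

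**Conclusion.** The point holds in a limited form. As the protocol text stands, adverse events are actively asked about only at a requested withdrawal; among caregivers who stay in, they are known only if volunteered or noticed. This could concern up to 25 caregivers. It rests on a reading of the text and on no assumed number, but it is conditional on the unseen manual. If the manual already contains a systematic check, the sponsor need only cite it and report the tally.

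No figure in the plan is shown to be wrong, and the primary feasibility conclusion is unaffected. The change is worth considering because it is cheap and improves both safety information and the exit feedback that the aim relies on.

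**What to change.** 1. Add one question to 31.09, put to every participant at the existing exit contact, and at a withdrawal contact if the caregiver agrees: *Did you have any adverse event, or feel worse, during the study?*
2. Route positive answers into the 14.0 pathway, and keep a simple log of each time that pathway is used.
3. In 11.2, add a descriptive line reporting the number with an event or feeling worse (out of the number asked, with an exact 95% confidence interval), the number for whom 14.0 was activated, and the number not asked.
4. State that a single-arm pilot cannot separate an effect of the intervention from the effect of the patient's decline.
5. Do not add a HADS cutoff-crossing count as a harm measure.

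Cost: one extra question, a few follow-up contacts and one line of descriptive results, with no new instrument or visit. The price is a count that will be imprecise and cannot be attributed to the intervention.
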